9.4.3 Method of Assigning Subjects to Treatment Groups

The three test materials will be assigned randomly to the test sites per a computer-generated randomization schedule, such that two of the three test materials are used on each subject at the abdomen and/or inguinal sites, one test material on one side, and another test material on the opposite side of the subject. The randomization schedule will be continued until it is determined that the required sample sizes are fulfilled.

The specific sites for post-application sampling (i.e., 30 seconds, 10 minutes, and 6 hours after skin preparation on the abdominal and inguinal test sites) will be assigned according to a computer-generated randomization scheme.

9.4.4 Pre-Test Conditioning Period

The 14 days prior to the test portion of the study will constitute the pre-test period. During this time, subjects will avoid the use of medicated soaps, lotions, deodorants and shampoos, as well as skin contact with solvents, detergents, acids and bases, or any other products known to affect the normal microbial populations of the skin. Subjects will be supplied a personal hygiene kit containing non-medicated soap, shampoo, antiperspirant, lotion, and rubber gloves to be worn when contact with antimicrobials, solvents, detergents, acids, or bases cannot be avoided. Subjects will be instructed to use the contents of this kit exclusively during their participation in the study. Subjects must also avoid using UV tanning beds or sunbathing and swimming or bathing in biocide-treated pools or hot tubs.

At least 3 days (72 hours) prior to the test period, the subjects will be examined physically to ensure that there is no evidence of injury, dermatosis, or dermatitis present on the test areas. Hair present on test areas may be clipped if needed, to ensure that bandages used in testing will remain secure to the test sites.

9.4.5 Test Period

Prior to sampling, the subjects will be questioned regarding adherence to the protocol. Females must have a negative urine pregnancy test documented before treatment with test materials. Subjects will don a disposable undergarment prior to sampling and will be examined physically to ensure no evidence of injury, dermatosis, or dermatitis is present at the sampling sites. Subjects will also don disposable exam gloves prior to product application to guard against contamination of the test sites during testing.

On the abdomen (dry-skin sites), a sterile surgical marker will be used to demarcate bilaterally two 5" x 5" areas of skin (Appendix 1) that appear to be similar in condition, and not including the waistband area of clothing the subject was wearing, to the right and left side of the navel. In the inguinal region (moist-skin sites), a sterile surgical marker will be used to demarcate bilaterally two 1.5" x 5" areas of skin (Appendix 1) that appear to be similar in condition.

Subjects will be sampled for baseline microbial population at the abdominal and inguinal sites on both sides using the Cylinder Sampling Technique (Section 9.4.7).

The randomly assigned test materials will be applied to the abdominal and inguinal test sites per directions presented in Appendix 2. All test materials, including packaging, will be weighed before and immediately following application (Appendix 2) and the weights will be recorded.

The abdominal and inguinal test sites will be sampled 30 seconds + 5 seconds (30 seconds to 35 seconds) and 10 minutes \pm 30 seconds post-product application using the Cylinder Sampling Technique (Section 9.4.7). At the completion of the 10-minute sample, the assigned 6-hour sample site will be covered with a dressing consisting of sterile gauze and semi-occlusive bandages to protect the site until the 6-hour sample window. All sampling times will be calculated from the completion of the dry time of each test material following application. Samples will be taken from the assigned sites at 6 hours \pm 30 minutes post-product application using the Cylinder Sampling Technique (Section 9.4.7). If the semi-occlusive bandage has lifted from a test site such that the gauze sponge is no longer secured, the test site will be sampled and the occurrence noted.

Each subject who volunteers to participate in this study will be required to remain/be sequestered at the test facility through the 6-hours post-treatment sampling. Following collection of the last 6-hour \pm 30 minutes post-product application sample of a test site, the remaining test material will be wiped/cleansed from the test site with a mild soap and/or tap water; test sites will be dried with paper towels.

9.4.6 Blinding

Technicians who participate in test material application or bacterial sample collections, will not be blinded to the test material identity due to the physical differences of the test materials.

Technicians who participate in plating samples and/or counting plates from samples will not participate in the test product application or sample collection procedures.

9.4.7 Cylinder Sampling Technique

A sterile cylinder with an inside area of 3.46 cm² will be held firmly onto the test site to be sampled. 3.0-mL of sterile Stripping Suspending Fluid with product neutralizers (SSF++) will be placed into the cylinder, and the skin area inside the cylinder will be massaged in a circumferential manner for 1 minute with a sterile rubber policeman. The SSF++ will be removed with a sterile pipette and transferred to a sterile test tube. A second 3.0-mL aliquot of SSF++ will be placed into the cylinder, and the skin area again massaged for 1 minute with a sterile rubber policeman. Both aliquots will be pooled together for enumeration of microorganisms.

9.4.8 Plating

Aliquots of the microorganism suspension (10⁰ dilution) will be serially diluted in Butterfield's Phosphate Buffer Solution with product neutralizers (BBP++), as appropriate. Triplicate pour-plates will be prepared from each of these dilutions in Tryptic Soy Agar with product neutralizers (TSA+) and incubated at 30 °C ± 2 °C for approximately 72 hours, or until sufficient growth is observed.

9.5 Efficacy and Safety Variables

Subject safety will be monitored by irritation evaluations and Adverse Event reporting (Section 11.0).

9.5.1 Efficacy and Safety Measurements and Flow Chart

Mean log₁₀ reductions in normal flora will be used to determine the antimicrobial effectiveness of the test materials.

Flow Chart

Procedure	Day		
	-14 or more	-14 to 0	0
Informed Consent Signed	X		
Inclusion/Exclusion Criteria Reviewed	X		X
Pre-Test Conditioning Period		X	
Evaluation of Skin Condition			X
Test Material Application Locations and Sampling Sites Assigned			X
Baseline Sample			X
Test Material Application			X
30-second Post-Application Sample			X
10-minute Post-Application Sample			X
6-hour Post-Application Sample			X

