2.0 PROTOCOL SYNOPSIS

Name of Sponsor: Professional Disposables International, Inc. (PDI)	Protocol Number 1810480-103.01
Name and Concentration of Test Product Active Ingredients: 26 mL Chlorhexidine Gluconate 3.15% (w/v) and Isopropyl Alcohol 70% (v/v) solution 5.1 mL Chlorhexidine Gluconate 3.15% (w/v) and Isopropyl Alcohol 70% (v/v) solution	
Title of Study:	Pilot Evaluation of Two Test Materials with a Positive Control When Used as a Patient Preoperative Skin Preparation
Principal Investigator:	[name]
Sub-Investigators:	[name], CCRC, [name], CCRP, [name], [name]
Study Center:	BioScience Laboratories, Inc.
Publications (References)	ASTM Standard Test Method E1173-15, Evaluation of Preoperative, Precatheterization, or Preinjection Skin Preparations ASTM E1054-08(2013), Standard Test Methods for Evaluation of Inactivators of Antimicrobial Agents . 2017 FDA, 21 CFR Part 310, Safety and Effectiveness of Health Care Antiseptics; Topical Antimicrobial Drug Products for Over-the-Counter Human Use , Final Rule. (FR82: No. 243, December 20, 2017. pp 60474 to 60503)
Study Duration:	A pre-test period of 14 days and a test period of 1 day.
Objectives:	The purpose of this pilot study is to evaluate the antimicrobial efficacy of two test products containing a chlorhexidine gluconate and isopropyl alcohol solution (26 mL and 5.1 mL), when used as a patient preoperative skin preparation compared to a positive control (Prevantics® Maxi Swabstick 5.1 mL). The evaluation will determine the correct application procedures and the sample size to be used for the pivotal study. The \log_{10} recoveries of the normal flora will be used to determine the antimicrobial effectiveness of the two test materials using a multiple linear regression model, consistent with the requirements of the 2017 FDA 21 CFR

Name of Sponsor: Professional Disposables International, Inc. (PDI)	Protocol Number 1810480-103.01
Name and Concentration of Test Product Active Ingredients: 26 mL Chlorhexidine Gluconate 3.15% (w/v) and Isopropyl Alcohol 70% (v/v) solution 5.1 mL Chlorhexidine Gluconate 3.15% (w/v) and Isopropyl Alcohol 70% (v/v) solution	
	Part 310, Safety and Effectiveness of Health Care Antiseptics; Topical Antimicrobial Drug Products for Over-the-Counter Human Use , Final Rule (December 20, 2017); the difference between the two regression lines is the Average Treatment Effect (ATE).

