Criteria for Evaluation:	
Efficacy: The primary efficacy variables for this study are the immediate antimicrobial effects at 30-seconds and 10-minutes post-application and persistent antimicrobial effects at 6-hours post-application. The effectiveness criteria are that the \log_{10} recoveries of the two test products (26 mL and 5.1 mL) are non-inferior to the Positive Control (Prevantics® Maxi Swabstick 5.1 mL) with a 0.5 margin (\log_{10} scale) per square centimeter on the abdominal and inguinal sites within 30 seconds after drying and within 10 minutes after drying. The determination of non-inferiority will be based on a \log_{10} multiple linear regression model. The Average Treatment Effect (ATE) is the mean difference of the test and the positive control products used in performing a non-inferiority statistic. To demonstrate persistence for the test materials, the 6-hour post-treatment measurement should be lower than or equal to the baseline measurement for 100 percent of the subjects on the abdominal and inguinal sites. The efficacy criteria will be consistent with the requirements of the 2017 FDA 21 CFR Part 310, Safety and Effectiveness of Health Care Antiseptics; Topical Antimicrobial Drug Products for Over-the-Counter Human Use, Final Rule (December 20, 2017).
 
Safety: Evaluation for safety of use of the test materials will consist of Adverse Event-reporting and assessment for skin reactions during testing.

Name of Sponsor: Professional Disposables International, Inc. (PDI)
	

Name and Concentration of Test Product Active Ingredients: 26 mL Chlorhexidine Gluconate 3.15% (w/v) and Isopropyl Alcohol 70% (v/v) solution 5.1 mL Chlorhexidine Gluconate 3.15% (w/v) and Isopropyl Alcohol 70% (v/v) solution
	
Protocol Number 1810480-103.01

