
Statistical Methods:
	
A statistical analysis of the data will be performed to determine the non-inferiority of the two test products to the Positive Control. Separate analyses will be performed for data sets for the abdomen and the inguinal test sites and for the 30-seconds and 10-minutes post-application sample times. The statistic to be used is a multiple linear regression with one quantitative and one qualitative variable. The average treatment effect (ATE) is the mean difference of the two products with the 95% confidence intervals in place that will determine if the test products will pass the non-inferiority evaluation. To pass, the upper bounds of the 95% confidence interval must be equal to or less than $0.5 \log_{10}$. The number of subjects necessary to pass this requirement will be determined.
 
Descriptive statistics will be generated, including sample sizes, means, standard deviations, and ranges.

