4.0 LIST OF ABBREVIATIONS AND DEFINITIONS OF TERMS

AE	Adverse Event
ASTM	American Society for Testing and Materials
ATCC	American Type Culture Collection
ATE	Average Treatment Effect
BBP++	Butterfield's Phosphate Buffer Solution with product neutralizers
BSLI	BioScience Laboratories, Inc.
CFR	Code of Federal Regulations
CFU	Colony Forming Units
CHG	Chlorhexidine gluconate
cm	Centimeter
CRF	Case Report/Record Form
CRO	Contract Research Organization
FDA	Food and Drug Administration
FR	Federal Register
GCP	Good Clinical Practice
GLP	Good Laboratory Practice
GIRB	Gallatin Institutional Review Board
HIPAA	Health Insurance Portability and Accountability Act
ICH	International Conference on Harmonization
in	Inch
mL	Milliliter
PBS	Phosphate Buffered Saline
SAE	Serious Adverse Event
SD	Standard Deviation
SSF++	Stripping Suspending Fluid with product neutralizers
SOP	Standard Operating Procedure
TSA	Tryptic Soy Agar
TSA+	Tryptic Soy Agar with product neutralizers
TSB	Tryptic Soy Broth

PROTOCOL #1810480-103.01

Page 9 of 43

BIOSCIENCE LABORATORIES, INC.

This Protocol has been approved by the GIRB on

03/06/19

TFM	Tentative Final Monograph
UV	Ultraviolet
Cylinder Sampling Procedure	A procedure used to sample bacteria from the skin using a sterile cylinder, sterile rubber policemen and a specified volume of sampling fluid.
Mean \log_{10} reductions	Average of the differences between the baseline microbial populations expressed as \log_{10} CFU/cm ² and the populations in \log_{10} CFU/cm ² recovered from the post-application samples.
Positive Control	A product that is to be tested according to procedures in this protocol in order to validate the testing procedures and to be used as a control.
Source Documents	Recorded results of original observations and activities of a clinical investigation.
Subjects	Healthy human paid participant that has consented to test in the study.
Test Material	The test products or positive control that are to be tested according to procedures in this protocol.

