8.0 STUDY OBJECTIVES

The purpose of this pilot study is to evaluate the antimicrobial efficacy of two test products containing a chlorhexidine gluconate and isopropyl alcohol solution (26 mL and 5.1 mL), when used as a patient preoperative skin preparation. The evaluation will determine the correct application procedures and the number of subjects needed to pass the pivotal study. The \log_{10} recoveries of the normal flora will be used to determine the antimicrobial effectiveness of the two test products consistent with the requirements of the 2017 FDA 21 CFR Part 310, *Safety and Effectiveness of Health Care Antiseptics; Topical Antimicrobial Drug Products for Over-the-Counter Human Use*, Final Rule (December 20, 2017).

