9.7.1 Statistical Methods

The Minitab® Version 18 statistical computer package will be used for all statistical calculations.

Non-Inferiority Analysis

An analysis of the data will be performed to determine the non-inferiority of the two test products to the Positive Control. Separate analyses will be performed for data sets for both the abdomen and the inguinal test sites and for the 30-seconds and 10-minutes post-application sample time. Only those data from sites meeting the baseline criteria (3.0 - 5.5 \log_{10} CFU/cm² from the skin of the abdomen and 5.0 - 7.5 \log_{10} CFU/cm² from the skin of the inguen) will be used in the analysis.

The statistic to be used is a multiple linear regression with one quantitative and one qualitative predictor. It has the form:

$$\hat{y} = B_0 + B_1 x_1 + B_2 x_2 + e$$

where:

\hat{y} = \log_{10} Recoveries

B_0 = y intercept

B_1 = Regression slope

B_2 = Difference between the two products

x_1 = \log_{10} Baseline

x_2 = Products

1, if Test Product

2, if Positive Control

e = Error term

The average treatment effect (ATE) is the mean of the 95% confidence interval. For the non-inferiority test, the upper bound of the 95% confidence interval must be equal to or less than 0.5 \log_{10} .

For the non-inferiority test:

$$\bar{x}_C - \bar{x}_T \leq 0.5$$

where:

\bar{x}_T = mean of the test product

\bar{x}_C = mean of the positive control product

0.5 = non-inferiority margin

Descriptive statistics will be generated, including sample sizes, means, standard deviations, and ranges of the recovery data.

Sample Size Determination Analysis

When the study is complete, the PASS 16 statistical package will determine the number of subjects used in a pivotal study for the abdominal and inguinal regions.

The formula that will be used is:

$$n \geq \frac{2 s^2 (z_{\alpha/2} + z_{\beta})^2}{0.5^2}$$

where:

n = minimum number of subjects employed in the study

2 = number of products tested; 3 test materials (Test Product #1, Test Product #2 and Positive Control)

s^2 = the largest variance of the two products tested at the abdominal or inguinal sites

$z_{\alpha/2} = 1.96$ (z-scale) for $1 - 0.05 = 95\%$ confidence of Type I error

$z_{\beta} = 0.842$ (z-scale) for $1 - 0.20 = 0.80\%$ confidence of Type II error

0.5 = Detection level requirement

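### Section 9.5.1 bases effectiveness on unadjusted mean log10 reductions, while 9.5.3 and 9.7.1 base non-inferiority on log10 recoveries, and the sign of the 9.7.1 inequality does not settle the conflict

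*Combined protocol and SAP*

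**What the plan says.** Section 9.5.1 states that mean log10 "reductions in normal flora will be used to determine the antimicrobial effectiveness of the test materials". Mean log10 reduction is a defined term in section 4.0: the "Average of the differences between the baseline microbial populations expressed as" log10 CFU/cm² and the post-application populations on the same scale. No covariate enters that definition.

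Section 8.0 uses almost the same sentence for another quantity: log10 "recoveries of the normal flora will be used to determine the antimicrobial effectiveness of the two test products". The synopsis (Objectives) also says log10 "recoveries of the normal flora will be used to determine the antimicrobial effectiveness of the two test materials using a multiple linear regression model". Sections 9.1, 9.5.2 and 9.5.3 and the synopsis (Criteria for Evaluation) attach the 0.5 log10 margin to recoveries. Section 9.5.3, which is headed as the primary efficacy variables, rests the decision on the regression and the 95% interval around the ATE.

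Section 9.7.1 gives the model: "The statistic to be used is a multiple linear regression with one quantitative and one qualitative predictor". The outcome is log10 recoveries, the quantitative predictor is log10 baseline, and product is coded 1 for test and 2 for positive control. It then states the non-inferiority condition as control mean minus test mean at most 0.5.

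**The concern.** Two near-identical sentences name different measures as the basis of effectiveness, and nothing gives one precedence. A change from baseline and a baseline-adjusted follow-up value estimate the same product effect on average in a randomised comparison. In a given data set, however, they can differ in both estimate and interval width.

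The natural reply is that 9.7.1, as the detailed analysis section, settles it. Its inequality weakens that reply. A higher recovery is worse, so non-inferiority on recoveries needs test minus control to be bounded above. Control minus test is the right direction for reductions, where higher is better. The mixture of the two measures therefore reaches the decision rule itself.

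**Working it through.** **The plan's own figure.** 75 subjects × 2 sides ÷ 3 materials = 50 sites per material, as stated in the synopsis. No SD or slope is given, so everything below that needs one is an assumption.

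**How the two contrasts relate.** Let B1 be the slope of recovery on baseline and d the test-minus-control difference in mean baseline.
- Adjusted recovery contrast (test − control): Δ = (recovery difference) − B1·d.
- Unadjusted reduction contrast (control − test): (recovery difference) − d = Δ − (1 − B1)·d.

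Both are oriented so that positive means the test product is worse. They coincide only if B1 = 1 or d = 0. Section 9.5.4 sets values below 1 CFU/cm² to 1, so recoveries at that floor do not vary with baseline, which pulls B1 below 1. If reductions were fitted with the same baseline covariate, the bounds would be identical (differences below 1e-13). The conflict arises from the unadjusted definition in 4.0.

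**Worked reversals.** Assume residual SD 1.0, baseline SD 0.6, B1 = 0.3, n = 50 per material. The SD of a reduction is √(1.0² + 0.7² × 0.6²) = 1.085. With |d| = 0.2, the 95% half-widths are 0.402 (adjusted recoveries) and 0.430 (reductions).

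| Case | Recoveries: upper bound | Reductions: upper bound |
|---|---|---|
| Δ = 0.05, d = −0.2 | 0.05 + 0.402 = 0.45, pass | 0.05 + 0.14 + 0.430 = 0.62, fail |
| Δ = 0.15, d = +0.2 | 0.15 + 0.402 = 0.55, fail | 0.15 − 0.14 + 0.430 = 0.44, pass |

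The standard error of d is 0.6 × √(2/50) = 0.12, so an imbalance of at least 0.2 in either direction occurs in roughly 10% of comparisons.

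**How often verdicts differ.** Simulation with true difference 0, independent sites and 6,000 runs per setting:
- Residual SD 0.9, baseline SD 0.6, B1 = 0.3: pass rates were 79% (adjusted recoveries) and 70% (reductions). Verdicts differed in 14% (13.4% in a repeat), and the estimates differed with SD 0.086 log10.
- Over baseline SD 0.4 to 0.72, residual SD 0.7 to 1.1 and B1 of 0, 0.3 and 0.6, verdicts differed in 2.5% to 26.3%.

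A second grid (2,000 runs per setting, baseline SD 0.5 and 0.7, residual SD 0.8 to 1.2, true difference 0 or 0.2) gave about 4% to 25% for B1 from 0 to 0.6, and about 1% to 3% at B1 = 1.

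**The sign in 9.7.1.** With product coded 1 = test and 2 = control, B2 is control minus test. Suppose the test product leaves recoveries 1.0 log10 higher than control. Control minus test is then −1.0, and with a half-width of about 0.40 the upper bound is about −0.60, which satisfies the limit of 0.5. In simulation this rule, read literally on recoveries, passed such a product in 100% of runs. Test minus control passed it in 0%.

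**Carry-over to pivotal sizing.** The 9.7.1 formula gives n = 2 × (1.96 + 0.842)² ÷ 0.5² × s² = 62.8 × s². Section 9.7.1 does not say whether s² is the variance of recoveries or of reductions, although its descriptive statistics are for recoveries. At residual SD 1.0 and baseline SD 0.6 the two choices give 63 against 86 at B1 = 0, 65 against 74 at B1 = 0.3, and 86 against 63 at B1 = 1.

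**The case against.** The strongest reply is that the decision rule is already settled. Section 9.5.1 is one sentence above a flow chart. It does not use the word primary and gives no contrast, margin or interval. Section 9.5.3 defines the primary variables through recoveries and the regression, every statement of the 0.5 margin attaches to recoveries, and no non-inferiority analysis of mean reductions is specified anywhere. This largely stands. A reader might infer that the plan sets up two rival primary measures and leaves a free choice after the data are seen. The documents do not support that, because testing reductions against the margin would depart from 9.5.3 and 9.7.1. What survives is an operative efficacy statement that contradicts them, together with an inequality in 9.7.1 whose sign fits the other measure.

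A reader might also infer that the ATE is defined twice, once adjusted and once not. The synopsis says "the difference between the two regression lines is the Average Treatment Effect (ATE") in one place, and in another that the ATE "is the mean difference of the test and the positive control products used in performing a non-inferiority statistic". The second phrase directly follows a sentence resting the decision on the regression, and with parallel lines the distance between them is the adjusted mean difference. Even an unadjusted reading would concern recoveries, not reductions. The wording is loose but not a second definition.

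Nor do the synopsis and 8.0 themselves specify baseline-adjusted recoveries. Section 8.0 mentions no adjustment, and the synopsis says only "The statistic to be used is a multiple linear regression with one quantitative and one qualitative variable". Baseline is named as the covariate in 9.7.1 alone.

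On size, each subject receives two of the three materials (9.4.3), so treating sites as independent probably overstates baseline imbalance. With assumed within-subject correlations of 0.8 for baseline and 0.3 for residual, disagreement in the setting with residual SD 0.9 falls from 13.4% to 10.8%. At a true difference of 0.5 the pass rate is about 2.5% under either measure, so neither, fixed in advance and correctly signed, inflates false non-inferiority.

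**Conclusion.** The contradiction is real and should be corrected. Section 9.5.1 names unadjusted mean reductions as determining effectiveness, while 9.5.3 and 9.7.1 rest non-inferiority on recoveries. The intended measure is fairly clear, and 9.5.1 is the outlier. The sign of the 9.7.1 inequality keeps that section from closing the question.

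If reductions were analysed as 4.0 defines them, verdicts would differ from the adjusted-recovery analysis in roughly 2% to 26% of comparisons for B1 between 0 and 0.6, and rarely at B1 = 1. Those rates depend on assumed SDs and slopes and on independent sites, so they indicate scale and do not predict this study. The contradiction and the sign problem rest on the text alone. This is a pilot, so the practical consequences are a pilot pass or fail that depends on the measure used and, if the variance follows the wrong measure, a different pivotal sample size.

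**What to change.** - In 9.5.1, replace the mean-log10-reductions wording with: *log10 recoveries of the normal flora, adjusted for log10 baseline by the 9.7.1 regression*.
- State there that mean log10 reductions, as defined in 4.0, are descriptive only and do not enter the non-inferiority decision.
- Define the ATE once, as the baseline-adjusted test-minus-control difference in log10 recoveries, and use that definition in the synopsis, 9.5.3 and 9.7.1.
- In 9.7.1, align the coding and inequality with that sign, for example 0 = positive control and 1 = test product, with the upper 95% limit of test minus control at most 0.5. Defining the ATE as B2 without changing the present coding would fix the wrong sign in place.
- In the same edit, say which variance enters the pivotal sample-size formula.

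The cost is protocol wording, with no new subjects, samples or data. The only downside is that mean reductions can no longer be quoted as a basis for effectiveness.

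### The plan does not withhold the product-to-side allocation from unblinded sample collectors until the baseline sample is taken, which leaves an avoidable opportunity for bias in the baseline count

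*Combined protocol and SAP*

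**What the plan says.** **Order of steps.** The flow chart (section 9.5.1) puts "Test Material Application Locations and Sampling Sites Assigned" immediately above the baseline sample, both on Day 0. The rows after it (baseline, application, 30 seconds, 10 minutes, 6 hours) run in time order.

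**Assignment.** Section 9.4.3 states: "The three test materials will be assigned randomly to the test sites per a computer-generated randomization schedule". Two of the three materials go to each subject, one per side. The section gives no release time, no holder of the schedule and no concealment step. It randomises "The specific sites for post-application sampling" but does not mention the baseline cylinder position.

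**Test day.** Section 9.4.5 states: "Subjects will be sampled for baseline microbial population at the abdominal and inguinal sites on both sides using the Cylinder Sampling Technique". It continues: "The randomly assigned test materials will be applied to the abdominal and inguinal test sites". It does not say when the allocation becomes known.

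**Blinding.** Under section 9.4.6, staff who apply material or collect samples "will not be blinded to the test material identity due to the physical differences of the test materials". Plating and counting are done by other staff.

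**Use of the baseline count.**
- Gate: "Only those data from sites meeting the baseline criteria" enter the analysis (section 9.7.1; also 9.5.4). The windows are 3.0 to 5.5 log10 CFU/cm² for the abdomen and 5.0 to 7.5 for the inguen.
- Covariate: log10 baseline is the quantitative predictor in the regression of section 9.7.1.
- Reference: the 6-hour count must not exceed baseline in any subject (section 9.5.3).

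**The concern.** The reason given for not blinding is that the materials look different. That reason applies once a material is opened. It does not apply at baseline, when nothing has been opened. Unblinded collection after application may be unavoidable here, but unblinded collection at baseline is not.

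Baseline recovery is operator-dependent: two one-minute manual massages inside a cylinder (section 9.4.7), at a position the text does not fix. A collector who knows which side will receive the test product could, without intending to, work the two sides differently. Because one number has three uses, a one-sided shift would affect which sites are analysed, the adjusted product difference and the 6-hour criterion. On the 6-hour criterion the shift counts in full, because the 6-hour count is compared directly with baseline.

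**Working it through.** **1. The plan's own figure.** 75 subjects × 2 sides / 3 materials = 50 sites per material in each region, as the synopsis states. This is the n used in step 3. The concern itself rests on no stated figure.

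**2. Effect through the covariate.** Write T = 1 for a test-product site and 0 for control, τ for the true test-minus-control difference in log10 recovery, and B1 for the baseline slope. If the recorded baseline equals the true baseline plus d on test sites only, then

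y = B0 + B1·x_true + τT + e = B0 + B1·x_recorded + (τ − B1·d)T + e.

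The adjusted difference moves by −B1 × d, which favours the test product when B1 and d are positive. Section 9.7.1 writes the contrast as control minus test; the size of the movement is the same either way. The documents give neither B1 nor d, so both are assumed:

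| B1 | d = 0.1 | d = 0.2 | d = 0.3 | d = 0.5 |
|---|---|---|---|---|
| 0.2 | 0.02 (4%) | 0.04 (8%) | 0.06 (12%) | 0.10 (20%) |
| 0.5 | 0.05 (10%) | 0.10 (20%) | 0.15 (30%) | 0.25 (50%) |
| 0.8 | 0.08 (16%) | 0.16 (32%) | 0.24 (48%) | 0.40 (80%) |
| 1.0 | 0.10 (20%) | 0.20 (40%) | 0.30 (60%) | 0.50 (100%) |

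Entries are log10 units, with the share of the 0.5 margin in brackets. Since 10^0.2 ≈ 1.6 and 10^0.3 ≈ 2.0, d = 0.3 means twice the yield on one side only.

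**3. Effect on the non-inferiority decision.** The planned regression was simulated 6,000 times per setting with the abdominal gate, 50 sites per material treated as independent, and a product truly at the 0.5 margin. Assumed: residual SD 0.9, true baseline mean 4.0 and SD 0.8. The chance of passing was:
- no shift: 2.2% (B1 = 0.5) and 2.6% (B1 = 0.8), close to the nominal 2.5%;
- d = 0.2: 7.9% (B1 = 0.5) and 14.4% (B1 = 0.8).

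**4. Effect through the gate.** Normal tail areas outside 3.0 to 5.5 give the share of abdominal sites failing, without and with a shift of +0.2:

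| Assumed mean, SD | No shift | +0.2 |
|---|---|---|
| 3.6, 0.7 | about 20% | about 13% |
| 4.0, 0.8 | about 14% | about 12% |
| 4.5, 0.7 | about 9% | about 13% |

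The direction depends on where the assumed mean lies in the window. The documents give no mean or SD.

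**The case against.** **The sequence is inferred.** It rests on row order within one Day 0 column. The chart does not say that its rows are chronological, and it is not a full schedule: it shows skin evaluation only on Day 0, although section 9.4.4 requires an examination at least 72 hours before the test period and section 11.2 requires scoring at every sample time. Section 9.4.6 also does not say that the collector sees the side allocation at baseline. This stands as a limit on certainty. It does not remove the point, because if the row order means nothing, the plan is simply silent on concealment and the same wording is needed.

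**Safeguards exist.** Cylinder, fluid volume and massage time are fixed. Plating and counting are done by separate staff, samples carry the subject's study number (section 15.1), and counts are read after about 72 hours, so the collector gets no immediate feedback. These protect counting and limit the room for influence. They do not cover how the sample is collected.

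**The direction may reverse.** If the same staff worked the test side harder at baseline and again after application, the net movement would be about d × (1 − B1), which is against the test product when B1 is below 1. Effort after application enters the outcome with coefficient 1, and this fix does not touch it. Both statements are correct.

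**It is a pilot.** The pivotal sample-size formula uses the variance of the products, and a constant baseline shift does not change the post-application recoveries themselves. The non-inferiority and 6-hour criteria remain exposed.

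A reader might infer that the plan biases results toward the test products, or take the percentages of the margin as estimates. The documents support neither: they give no slope, SD, baseline distribution or shift, and knowledge of the allocation creates only an opportunity.

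**Conclusion.** The point holds as a cheap improvement. The documents list assignment before baseline, leave collectors unblinded without a baseline exception, and nowhere conceal the allocation until a manually collected baseline has been taken.

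The size and direction of any bias cannot be derived from the documents. The relation slope × d holds for a shift confined to the baseline on test sides; the example of 0.10 log10 (20% of the margin) uses an assumed slope of 0.5 and an assumed d of 0.2. The pass rates also rest on the assumed SD, baseline distribution and independence of sites. The covariate and 6-hour routes carry the argument. A reader might infer that the gate always helps the test product, but under the assumed distributions above it can go either way.

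**What to change.** - **Sections 9.4.3 and 9.4.5, and the flow chart:** split the assignment row in two. Fix the cylinder positions, baseline as well as post-application, in advance. Release the product-to-side allocation only after baseline samples from both sides have been collected. Moving the whole row would be too blunt, because positions may need setting first so that the cylinders do not overlap. The Appendix 1 diagram was not available in the text reviewed, so any baseline position shown there should be checked.
- **Section 9.4.6:** limit the unblinding exception to steps after a material is opened.

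**Cost:** protocol wording, submitted as a written amendment under section 9.8, and release of the allocation within the test-day workflow. No added visits or samples. Unblinded collection after application remains and needs to be acknowledged as a limitation.
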